#### 9.3.6. Subgroup Analyses

Subgroup analyses of the primary and secondary endpoint will be made to assess consistency of the improvement from baseline across the following subgroups

• Age group: < 65 years vs  $\ge 65$  years

- Sex: female vs male
- Race: white vs black vs other
- Ethnicity: Hispanic vs not Hispanic
- Baseline GLP-1 RA: liraglutide vs semaglutide vs dulaglutide
- Baseline GLP-1 RA equivalent doses (adapted from Almandoz et al. 2020):
  - dulaglutide 0.75 mg and liraglutide 1.2 mg vs
  - o dulaglutide 1.5 mg, semaglutide 0.5 mg, and liraglutide 1.8 mg vs
  - dulaglutide 3 mg and semaglutide 1 mg vs
  - o dulaglutide 4.5 mg and semaglutide 2 mg, and
- Baseline HbA1c (≤8.0%, >8.0%).

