2.1. Multiplicity Adjustment

Multiplicity adjustment will not be implemented in this study.

3. Analysis Sets

For the purposes of analysis, the following analysis sets are defined:

Population/Analysis Set	Description
Screened population	All participants who signed informed consent
Modified intent-to-treat population (mITT)	• All participants who are exposed to at least 1 dose of study intervention
Efficacy Analysis Set (EAS)	• This analysis set will be used to estimate the efficacy estimand for the primary objective, and for all other (secondary, exploratory) endpoints.
	• Data obtained during the treatment period from the mITT population, excluding (1) participants who were inadvertently enrolled* and (2) data after permanent discontinuation of treatment or initiation of prohibited medication.
Safety Analysis Set (SS)	• This analysis will be used to assess the safety of study treatment
	• Data obtained during the Treatment Period from the mITT population, regardless of adherence to treatment or initiation of prohibited medication.

* An inadvertent enroller refers to a subject who does not meet inclusion/exclusion criteria but receives study intervention.

4. Statistical Analyses

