4.3.2. Main analytical approach

The primary objective based on the efficacy estimand defined in Section 1.1 will be evaluated using the EAS dataset (Section 3). The primary analysis model for HbA1c measurements over time will be a mixed model for repeated measures (MMRM).

The observed changes in HbA1c level from baseline (Visit 2 on Week 0) to each of the scheduled post-baseline visits (Visit 3 on Week 4, Visit 4 on Week 8, and Visit 5 on Week 12) of each participant are the dependent variable. The baseline HbA1c value is incorporated as a covariate, and the visits are treated as fixed effects.

Mean change from baseline at Week 12 will be estimated by least square means (LS means), with accompanying P-value and 95% CI.

Operationally, the hypothesis defined in Section 2 will be tested at a two-sided 0.05 level by performing the test on the least square mean of changes from baseline at Week 12.

An unstructured covariance pattern will be used to estimate the variance-covariance of the withinparticipant repeated measures. Parameters will be estimated by REML with the Newton-Raphson algorithm and using the Kenward-Roger method for calculating the denominator degrees of freedom.

In case the model fails to converge, the following covariance structures will be tested in the following order:

- 1. Heterogenous Toeplitz
- 2. Heterogeneous First Order Autoregressive
- 3. Heterogeneous Compound Symmetry
- 4. Toeplitz
- 5. First Order Autoregressive, and
- 6. Compound Symmetry

The first covariance structure that converges will be used.

Missing data will not be imputed because the maximum likelihood estimate is unbiased for this model in case of a Missing at Random (MAR) mechanism. The P-value obtained for the least

square means for change from baseline will be used to determine the statistical significance to achieve the primary objective.

HbA1c values and change from baseline in HbA1c will also be summarized by visit using descriptive statistics.

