4.4.2. Main analytical approach

The same analytical approach will be applied for all secondary endpoints as for the primary endpoint, which is detailed under Section 4.3.2.

For secondary endpoints, MMRM will include baseline HbA1c ($\leq 8.0\%$, >8.0%) category as a covariate instead of continuous baseline HbA1c.

Objective	Efficacy Measure	Analysis Conducted	Additional information
CGM parameters	Change from baseline in %TAR at Week 12	MMRM as specified in Section 4.3.2.	 MMRM with terms for: Visits Baseline HbA1c category (≤8.0%, >8.0%) Baseline %TAR
CGM parameters	Change from baseline in TAR at Week 12	MMRM as specified in Section 4.3.2.	 MMRM with terms for: Visits Baseline HbA1c category (≤8.0%, >8.0%) Baseline TAR
FSG	Change from baseline at Week 12 in FSG	MMRM as specified in Section 4.3.2.	 MMRM with terms for: Visits Baseline HbA1c category (≤8.0%, >8.0%) Baseline FSG
Weight	Change from baseline at Week 12 in weight	MMRM as specified in Section 4.3.2.	 MMRM with terms for: Visits Baseline HbA1c category (≤8.0%, >8.0%) Baseline weight

Table 2.	Summary	of the	analysis	of Seconda	ry Endpoints.

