Summary statistics will be provided for actual values by visit (Baseline, Week 4, and Week 12) and changes from baseline values by each post-baseline visit (Week 4 and Week 12). The odds for a subject to reach a composite endpoint of the recommended time in all three International CGM Consensus Guideline ranges will be compared between baseline and Week 12 by a logistic regression model. The model will also include, baseline HbA1c ($\leq 8.0\%$, > 8.0%), and baseline composite endpoint as fixed effect.

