4.5.1. Summary for the Analysis of Exploratory Measures

Objective	Relative to the efficacy measure	Analysis Conducted	Additional information
CGM parameters	Mean change in	MMRM model as	MMRM with terms for:
	TIR from baseline	specified in Section 4.3.2	• Visit
			• Baseline HbA1c category (≤8.0%, >8.0%), and
			• Baseline TIR as a covariate
CGM parameters	Mean change in	MMRM model as	MMRM with terms for:
	TBR from baseline at week 12	specified in Section 4.3.2.	• Visit
			• Baseline HbA1c category (≤8.0%, >8.0%), and
			• Baseline TBR as a covariate
CGM parameters	Mean change in TITR from baseline at week 12	MMRM model as specified in Section 4.3.2 .	MMRM with terms for:
			• Visit
			• Baseline HbA1c category (≤8.0%, >8.0%), and
			• Baseline TITR as a covariate
CGM parameters	ters Mean change in GV MMRM model as specified in		Separate MMRM model for all measures of GV.
	week 12	Section 4.3.2.	MMRM with terms for:
			• Visit
			• Baseline HbA1c category (≤8.0%, >8.0%), and
			• Baseline GV measure as a covariate
CGM parameters	Change in odds for reaching composite	Logistic regression model as specified	Logistic Regression with terms for:
	endpoint of all in ranges from baseline to week 12	in Section 4.5	• Visit

Table 3.	Exploratory measures not controlled for Type 1 error
----------	--

			 Baseline HbA1c category (≤8.0%, >8.0%), and Baseline composite endpoint as a covariate
CGM parameters	Mean change in mean 24-hr daily blood glucose from baseline at week 12	MMRM model as specified in Section 4.3.2.	 MMRM with terms for: Visit Baseline HbA1c category (≤8.0%, >8.0%), and Baseline mean 24-hr daily blood glucose as a covariate
CGM parameters	Mean change in estimated post- prandial glucose excursion from baseline at week 12	MMRM model as specified in Section 4.3.2.	 MMRM with terms for: Visit Baseline HbA1c category (≤8.0%, >8.0%), and Baseline estimated post-prandial glucose excursion as a covariate
CGM parameters	Mean change in estimated fasting glucose at week 12	MMRM model as specified in Section 4.3.2.	 MMRM with terms for: Visit Baseline HbA1c category (≤8.0%, >8.0%), and Baseline estimated fasting glucose as a covariate

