4.7. Other Analyses

4.7.1. Subgroup analyses

Subgroup analyses of the primary and secondary endpoint will be made to assess consistency of the improvement from baseline across subgroups.

The primary and secondary endpoints will be examined using the same MMRM model defined in Section 4.3.2. but additionally, a SUBGROUP term will be included as fixed effects. LS-means with their corresponding 95% CIs and P-values will be reported for the subgroups.

The following subgroups are defined:

- Age group: < 65 years vs ≥ 65 years
- Sex: female vs male
- Race: white vs black vs other
- Ethnicity: Hispanic vs not Hispanic
- Baseline GLP-1 RA: liraglutide vs semaglutide vs dulaglutide
- Baseline GLP-1 RA equivalent doses (adapted from Almandoz et al. 2020):
 - dulaglutide 0.75 mg and liraglutide 1.2 mg vs.
 - o dulaglutide 1.5 mg, semaglutide 0.5 mg, and liraglutide 1.8 mg vs.
 - dulaglutide 3 mg and semaglutide 1 mg vs.
 - dulaglutide 4.5 mg and semaglutide 2 mg
- Baseline HbA1c (<8.0%, >8.0%)

If the number of participants is too small (less than [10%]) within a subgroup, then the subgroup categories may be redefined prior to unblinding the study.

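### The subgroup MMRM holds the gap between subgroups equal at every visit, and no confidence interval or test for a between-subgroup difference is stated, although the aim is to assess consistency (minor, exploratory)

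*SAP*

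**What the plan says.** Protocol 9.3.6 gives the purpose: "Subgroup analyses of the primary and secondary endpoint will be made to assess consistency of the improvement from baseline across the following subgroups". SAP 4.7.1 repeats it and lists the same seven factors. Four have two levels (age, sex, ethnicity, baseline HbA1c), two have three (race, prior GLP-1 RA) and one has four (prior GLP-1 RA dose group).

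The model is the one in SAP 4.3.2, with visit and baseline HbA1c and no interactions, to which "a SUBGROUP term will be included as fixed effects. LS-means with their corresponding 95% CIs and P-values will be reported for the subgroups". For the primary analysis, 4.3.2 fixes the time point: "Mean change from baseline at Week 12 will be estimated by least square means (LS means". SAP 4.7.1 names no visit, no SUBGROUP-by-visit term, no between-subgroup difference and no heterogeneity test.

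For secondary endpoints, SAP 4.4.2 and Table 2 use the baseline HbA1c "category as a covariate instead of continuous baseline HbA1c". SAP 2.1 adds: "Multiplicity adjustment will not be implemented in this study".

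On a separate matter, SAP 4.5 says the odds of meeting the all-ranges composite "will be compared between baseline and Week 12 by a logistic regression model". Table 3 in 4.5.1 lists visit, HbA1c category and "Baseline composite endpoint as a covariate" as its terms.

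**The concern.** Consistency is a between-subgroup question. The planned output gives each subgroup its own mean change, CI and P-value against zero. Two subgroups that each differ from zero can differ clearly from each other, so these P-values cannot show consistency.

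The model also restricts what the LS means can show. HbA1c and weight enter at Weeks 4, 8 and 12, and TAR at Weeks 4 and 12. A SUBGROUP main effect fits one gap for all of those visits, so the Week 12 gap is partly set by the earlier visits. Protocol 4.2 justifies 12 weeks by the time HbA1c needs to reflect the switch. A gap in HbA1c response that is equal at Weeks 4 and 12 is therefore an assumption that needs support, and none is given.

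At stake are the planned results by prior GLP-1 RA and dose, in a study meant to tell providers what to expect after switching. The primary analysis is not touched.

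**Working it through.** **The plan's own figure.** One-sample t-test, N = 150, change 0.3, SD 1.1, two-sided 0.05 (SAP 5): power 91.3%, so the stated 90% is reproduced with 1.1 as the SD of the change. The SAP gives no figure for subgroups. The earlier-visit SDs, correlations, trajectories and subgroup splits below are assumptions.

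**Gap returned by the main-effect model.** With complete data and visit covariance V, the single contrast is w'd, where w = V⁻¹1 / (1'V⁻¹1) and d holds the true gaps by visit. SDs at Weeks 4/8/12 are (a) 1.1 throughout; (b) 0.9, 1.0, 1.1; (c) 0.7, 0.9, 1.1; (d) 0.5, 0.8, 1.1. Correlation is constant at 0.6, with AR(1) 0.6 in brackets. The constant-correlation weights are (a) 0.33/0.33/0.33, (b) 0.56/0.31/0.14, (c) 0.81/0.22/−0.03, (d) 1.04/0.09/−0.12. Example, steep growth in (c): 0.81×0.15 + 0.22×0.35 − 0.03×0.50 = 0.18.

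| True gap at Weeks 4/8/12 | (a) | (b) | (c) | (d) |
|---|---|---|---|---|
| 0.15/0.35/0.50 | 0.33 [0.33] | 0.26 [0.28] | 0.18 [0.22] | 0.12 [0.17] |
| 0.40/0.47/0.50 | 0.46 [0.45] | 0.44 [0.44] | 0.41 [0.42] | 0.39 [0.40] |
| 0.50/0.50/0.50 | 0.50 | 0.50 | 0.50 | 0.50 |
| 0.50/0.35/0.15 | 0.33 [0.33] | 0.41 [0.38] | 0.48 [0.43] | 0.53 [0.48] |
| 0.09/0.21/0.30 | 0.20 | 0.16 | 0.11 | 0.07 |

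The negative Week 12 weights in (c) and (d) depend on constant correlation; under AR(1) they are +0.15 and +0.06.

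**Effect on subgroup LS means at Week 12.** Each is the size-weighted Week 12 mean, plus or minus the contrast times the other group's share. Take steep growth and true changes of −0.50 and 0.00. At 75/75, pattern (a): −0.25 ± 0.33/2 = −0.42 and −0.08. At 135/15 the weighted mean is −0.45, and the small group (true 0.00) becomes −0.45 + 0.9×0.33 = −0.15 in (a) and −0.45 + 0.9×0.12 = −0.34 in (d).

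**TAR, two visits.** Set the Week 4 SD at 1.00 down to 0.45 of the Week 12 SD, correlation 0.6. If the Week 4 gap is 30% of the Week 12 gap, 65% down to 23% of the Week 12 gap is returned. If it is 80%, 90% down to 78% is returned.

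**Bias against precision.** The Week 12 interaction contrast has an SE 1.17, 1.32, 1.61 and 2.25 times the main-effect SE in (a) to (d) [1.22, 1.37, 1.64, 2.21]. Root-mean-square error is √(bias² + SE²).
- At 135/15 the interaction SE is 1.1√(1/135 + 1/15) = 0.30. With growth 0.09/0.21/0.30, the planned model gives 0.28, 0.27, 0.27 and 0.26, which is lower in every pattern.
- At 75/75 the interaction SE is 0.18. With steep growth in (d), the planned model gives √(0.376² + 0.080²) = 0.38, which is much worse.
- At 75/75 with mild growth, the planned model gives 0.16, 0.15, 0.14 and 0.13, which is lower.

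**P-values against zero.** With 75 per group and SD 1.1, each SE is 1.1/√75 = 0.127. Changes of −0.3 and −0.8 give p = 0.021 and p < 0.001. The direct comparison is 0.5/0.180 = 2.78, p = 0.006.

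**Duplicate term.** A secondary-endpoint model under 4.4.2 has three visit columns, the HbA1c category and the baseline measurement: rank 5. Adding SUBGROUP equal to that category leaves the rank at 5, so separate SUBGROUP LS means are not estimable.

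**Composite (separate point).** Assume 40% meet it at baseline, 90% of these keep it and 50% of the rest gain it: 0.4×0.9 + 0.6×0.5 = 66%. The marginal odds ratio is (0.66/0.34)/(0.40/0.60) = 2.9 and the paired one is 0.30/0.04 = 7.5. A large-sample logistic fit with visit and baseline composite (HbA1c category left out) gives 12.0, because on baseline rows that covariate is the outcome. For 50% to 65% (90% keep it, 40% gain it) it gives 5.1, against 1.86 and 4.0.

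**The case against.** Several stronger readings are tempting, and the documents do not support them.

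- A reader might infer that the subgroup LS means are not for Week 12. SAP 4.7.1 points to 4.3.2, which takes LS means at Week 12. Only the gap is constrained, and naming Week 12 is a clarification.
- A reader might infer that no between-subgroup estimate will exist. Subtracting two reported LS means gives a point estimate, and the table specifications are a separate document. What is missing is a stated CI and test. Protocol 9 assigns the technical description to the SAP, so the omission still matters there.
- A reader might infer that the planned model understates differences. It overstates a fading gap and is unbiased for a constant one. The Protocol 4.2 rationale makes a constant gap doubtful for HbA1c, but it does not establish growth.
- A reader might take the duplicated term as certain. Read literally, 4.7.1 cites 4.3.2, whose covariate is the continuous baseline value, and then nothing is duplicated. Duplication follows under 4.1 and 4.4.2.

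The best remaining defence is the trade-off. Pooling over visits buys precision, and in small subgroups or with mild change it can give the smaller total error. That stands. The steep case also assumes a gap of 0.50, larger than the whole effect of 0.3 in the sample-size section. The study is descriptive and single-arm, with no multiplicity control. None of this supplies a CI or test for the question that 4.7.1 sets itself.

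**Conclusion.** The point holds as a minor one on an exploratory analysis. The structural part needs no numerical assumption: a SUBGROUP main effect constrains the gap to be equal across visits for HbA1c, weight and TAR, and the stated P-values do not compare subgroups. FSG has one scheduled post-baseline visit, so the constraint does not bite there.

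The size does rest on assumptions. The documents give only the SD of 1.1. A Week 12 gap of 0.50 is returned as anything from 0.12 (steep growth, rising SDs) to 0.50 (constant), and a fading gap of 0.15 as 0.33 to 0.53. The interaction is therefore the better match to the question, but it does not always have the smaller error.

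For the baseline-HbA1c factor on secondary endpoints, 4.7.1 and 4.4.2 must be reconciled; under 4.4.2 the planned LS means cannot be produced. The composite logistic model is a distinct defect, with a distorted odds ratio and no within-participant correlation specified, and should be listed separately.

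**What to change.** In SAP 4.7.1:

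1. Add SUBGROUP-by-visit (not for FSG) and state that LS means are taken at Week 12.
2. For each factor, report one omnibus Week 12 heterogeneity P-value (all levels equal) and differences with 95% CIs. For the three- and four-level factors, take the differences against a prespecified reference level. Label all of this exploratory, unadjusted and low-powered, and say that non-significance is not evidence of consistency.
3. For the baseline-HbA1c factor on secondary endpoints, let SUBGROUP replace the category term. For HbA1c itself, note that the subgroup effect is conditional on continuous baseline HbA1c.

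The cost is one model term, a few contrasts and short notes, plus precision: an SE about 1.2 to 2.3 times larger under the assumed patterns. Power for a difference of 0.3 with SD 1.1 is about 38% at 75/75, 27% at 50/50, 21% at 37/37 and 17% at 135/15. The 95% CI half-width is about 0.35 at 75/75 and 0.59 at 135/15.

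Seven omnibus tests on four distinct endpoints (TAR minutes is a fixed multiple of %TAR) make 28, of which 28 × 0.05 = 1.4 would fall below 0.05 by chance. All pairwise differences would be 1+1+3+1+3+6+1 = 16 per endpoint, or 64 distinct, with about 3.2 by chance. That is a reason to prefer the omnibus test with a reference level.

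Listed separately, in SAP 4.5 and Table 3: drop the baseline composite covariate and fit a logistic GEE clustered on participant with visit and HbA1c category. This gives a marginal odds ratio, and the SAP should say so. The cost is one changed exploratory model.

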4.8. Interim Analyses

No interim analyses are planned for this study. If an unplanned interim analysis is deemed necessary for reasons other than a safety concern, the protocol must be amended.

4.8.1. Data Monitoring Committee (DMC) or Other Review Board

No DMC or other review board meeting is planned.

4.9. Changes to Protocol-Planned Analyses

There are no changes to protocol planned analyses.

5. Sample Size Determination

A sample size of 150 participants will provide at least 90% power to show an improvement in HbA1c from baseline at Week 12. This sample size is using the following assumptions:

- a 1-sample t-test with 2-sided significance level of 0.05
- within treatment difference from baseline at Week 12 is 0.3%, and
- intra-subject variability of 1.1%.

6. Supporting Documentation

6.1. Appendix 1: Demographic and Baseline Characteristics

A summary of demographics and baseline information will be presented. The demographic characteristics consist of age (in years), sex, race, and ethnicity. The baseline characteristics consist of baseline height (cm), baseline weight (kg), and Waist Circumference measurement (cm), fundoscopy exam results and substance use. All demographic and baseline characteristics will be presented in listings.

A participant's age in years is calculated using the date of the informed consent and date of birth. Age (years), baseline height (cm), baseline weight (kg), Waist Circumference measurement (cm), Systolic Blood Pressure (mmHg), Diastolic Blood Pressure (mmHg), and Pulse Rate (bpm) will be summarized using descriptive statistics.

The number and percentage of participants by age category (< 65 years vs \geq 65 years), sex (Male, Female), race (White, Black or African American, Asian, American Indian or Alaska Native, Native Hawaiian or Other Pacific Islander) and ethnicity (Hispanic or Latino, Not Hispanic or Latino), will also be reported.

Baseline fundoscopy results will be presented in a table for both eyes. For each eye respectively, number and percentage of participants with non-proliferative diabetic retinopathy will be presented by severity. Number and percentage of participants with proliferative diabetic retinopathy and macular edema will also be presented.

Percentages will be based on the total number of participants in the mITT set.

Collected data about substance use, including alcohol, caffein, recreational drugs, and tobacco will be listed.

6.1.1. Prior and Concomitant Medications/Therapy

All medications will be coded according to the World Health Organization drug dictionary

A prior medication/therapy is defined as those for which the end date is prior to the date of first study intervention administration or confirmed as 'not ongoing' by the participant before the start of study intervention. A concomitant medication/therapy is defined as any medication that has a stop date that is on or after the date of first dose of study intervention or confirmed as 'ongoing' by the participant at the start of study intervention. If a medication is not clearly indicated as ongoing nor the end date is documented, it will be treated as a concomitant medication.

For the purpose of inclusion in prior and/or concomitant medication tables, incomplete medication start and stop dates will be imputed as follows:

Missing start dates (where UK, UKN and UNKN indicate unknown or missing day, month and year respectively):

• UK-MMM-YYYY: Assume 01-MMM-YYYY. If the month and year are the same as the first dose of study intervention month and year, then assume the date of first dose of study drug.

- UK-UKN-YYYY: If the year is prior to the year of first dose of study intervention, assume 01-JAN-YYYY of the collected year. If the year is the same as the first dose of study intervention year, then assume the date of first dose of study intervention.
- UK-UKN- UNKN: Assume date of first dose of study intervention.

Missing stop dates for concomitant medications data will be handled as follows (where UK, UKN and UNKN indicate unknown or missing day, month, and year respectively):

- UK-MMM-YYYY: Assume the last day of the month.
- UK-UKN-YYYY: Assume 31-DEC-YYYY.
- UK-UKN- UNKN: Assume ongoing and leave it missing.

The total number of concomitant medications and the number and percentages of participants with at least one concomitant medication will be summarized. The number and percentages of all concomitant medications will be summarized and listed by Anatomical Therapeutic Chemical (ATC) level 4 and preferred term. Prespecified concomitant medications Acetaminophen / Paracetamol will be summarized in the same way.

The same summary will be presented for the prior medications/therapies as for concomitant medications.

The same summary will be presented for the background oral antihyperglycemic medications (OAMs), defined as medications belonging to the category of 'antihyperglycemics', taken via oral route, and starting prior to the start of study intervention.

All summaries will be performed using the Safety set.

